improvement training packages that will be delivered to more than 350 healthcare providers in 60 healthcare facilities in this program, with an appropriate performance framework to follow-up key-indicators around ANC-PNC, with regard to HIV, TB and malaria in particular.

Overall, with 6,936 ANC visits (of which 3,248 attending for the first/booking visit) and 826 PNC visits in the month of the survey – giving an estimate of 93,144 women annually – there is a wide scope for reaching a substantial population of women and babies to provide them with both basic services and disease-specific care.

There was good availability of services reported for the three diseases; 90% facilities offered HIV screening and 78.3% also offered treatment; 91.7% healthcare facilities offered malaria screening and treatment; 35% offered TB screening and treatment. However, it was evidenced that despite the full availability of rapid diagnostic tests for HIV (100%), the systematic screening for HIV in ANC was incomplete: HIV tests were conducted for 2,501 women at ANC (1,791 among them at booking visit – 55% of all women coming for ANC1) and 237 (28.7%) at PNC. Besides, 15.5% of women were tested for syphilis at ANC1, and none at PNC, even though 60% of healthcare facilities had rapid diagnostic tests. Furthermore, there was no screening for TB in ANC or PNC (1 woman - ~0%), suggesting that there are missed opportunities for identifying positive cases linked to the clinical screening and the decision to test women. For malaria, 413 (12.5%) women were tested for malaria at ANC and 17 (2.1%) at PNC with all those testing positive starting treatment. The high positivity rate among women tested (47.5%), suggested that the low proportion of women tested in ANC and especially in PNC could result in missed opportunities to identify and treat women. Again, there was a reported good availability of malaria testing kits (80%), therefore ruling out lack of availability as a sole explanation for this. Regarding provision of intermittent preventive treatment of malaria in pregnancy (IPTp), 54% of eligible women received prophylaxis in ANC, despite Sulfadoxine-pyrimethamine (SP) being found in 94.3% of healthcare facilities. This is indicative of the opportunity to improve the provision of basic and disease specific care.

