3.8 Statistical analysis

Period is defined as the assessment period of the trial which observation occurred, or for which measurement took place. Data will be omitted from analysis when values are missing for either the outcome or a covariate required for the analysis of that data value. Missing data will not be replaced.

For each ANC/PNC visit observed the proportion of essential components addressed will be calculated (ECall). Data analysis will be performed using Stata version 14.2 or later. To derive an estimate of the benefit of providing ANC-PNC training, linear regression within a generalised linear mixed model (GLMM) framework will be used to analyse the primary outcome data (ECall). GLMMs are appropriate in the context of stepped wedge trial designs as they allow for clustering and address confounding of intervention effects and time (Hemming et al 2015). The analysis will include a binary intervention factor which indicates if the data were collected pre- or post- ANC-PNC training and fixed effects for study month to account for any underlying secular trend. Random effects will be included for HCF (cluster), HCP within HCF and HCF by month interaction. The effects of the intervention will be reported as an adjusted (for month, HCF and HCF by month clustering) odds ratios (OR), with 95% confidence intervals.

Reporting will follow CONSORT guidelines for reporting stepped wedge trials current at the time of publication of the results (currently Hemming et al, 2018), Available data will be analysed using an intention to treat approach and also as implemented, if there are any protocol deviations, to assess the sensitivity of results to the analysis approach adopted.

The baseline delivery of essential components has been assumed to be around 50% as the precision of estimates is poorest for this value. If the level is below 50% there will be greater potential for improvement and greater power to detect an improvement of a specified magnitude. However, if the level is close to 100% it will not be possible for a statistically significant benefit of the intervention to be demonstrated. In such circumstances administrative analyses will be conducted.

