Appendix 2: Tools for data collection for observation

Below is the observation checklist. Essential components are numbered slightly differently than appendix 1 for the construction of the score. The scoring attributes will not appear for the data collectors and only be used by the statistician at time of analysis. Each essential component is score 1, for a total of 13 essential components for ANC visits, and 16 for PNC visits. Essential components can be a sum of x number of subcomponents as indicated in the table. Each subcomponent needs all applicable questions to be observed (Please see examples of algorithms at the end of appendix).

Please note this tool is to be deployed on an electronic platform, therefore the formatting of the tool will be visually different to what is included here. All boxes starting with "If" will only appear depending on the answer to the relevant condition (e.g. treatment will only be asked for women tested positive). The "Not applicable" answer is available for questions which depend on the gestational age and type of visit. The tool will be deployed in FRENCH.

OBSERVATION

Variable label	Answers	Conditionality	Scoring
GENERAL			
Please select the region	[dropdown menu]		
Please select the name of the facility	[dropdown menu]		
If 'Other' facility, please specify	[free text]		
Date of survey	[select from calendar]		
Name of person completing form	[free text]		
Anonymous ID of HCP	[free text]		
ANC			
ANC general information			
First/subsequent contact	0 - Subsequent contact, 1 - first contact -99 INF		
Which subsequent visit was it?	2- ANC2, 3- ANC3, 4- ANC4, 5- ANC5, 6-ANC6, 7- ANC7, 7-ANC8	Only to appear if previous answer = 0 – Subsequent visit	
Gestational age (weeks)	[integer]		
Who gave information about gestational age	1 - Woman, 2 - Healthcare provider, 3 - Other (specify)		
If other, specify	[free text]		
Women arrival time in the facility	[time]		
Comments	[free text]		

ANC contact		
EC1: Respectful maternity		1 (sum of all
care		subcomponents)
RMC subcomponent 1		0.25 (Points given if all applicable questions are observed)
The healthcare provider		
(HCP) introduced		
themselves to the		
pregnant woman	0 - No, 1 - Yes	
The HCP greeted the		
pregnant woman (or		
answered if woman		
greeted first)	0 - No, 1 – Yes	
RMC subcomponent 2		 0.25
The HCP asked the		
pregnant woman to take a	0 - No, 1 - Yes, -88 - Not	
seat	applicable (no chairs)	
The HCP asked the		
pregnant woman if she		
came with a companion		

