upon abnormal findings	findings)	Only on a care	
The HCP listened to foetal		Only appears	
movements		if age of	
	O No 1 Voc	pregnancy >	
If footal boombook linton and	0 - No, 1 - Yes	10 weeks	
If foetal heartbeat listened	O No 1 Voc 99 Not		
to, HCP recognised and acted upon abnormal	0 - No, 1 - Yes, -88 - Not		
findings	applicable (no abnormal findings)		
HCP asked the woman if	illialligs)		
she feels foetal	0 - No, 1 - Yes, -88 - Not		
	applicable		
If you HCD recognised and			
If yes, HCP recognised and acted upon abnormal	0 - No, 1 - Yes, -88 - Not		
· ·	applicable (no abnormal		
findings HCP did abdominal	findings)		
palpation	0 - No, 1 – Yes		
After abdominal palpation,	0 - No, 1 - Yes, -88 - Not	Only appears	
HCP recognised and acted	applicable (no abnormal	if previous	
upon abnormal findings	findings during	answer = 1-	
apon abnormal midnigs	examination)	Yes	
EC13 = Provide advice on	CAUTITIONOTI	103	1
birth preparedness and			_
danger signs of pregnancy			
Birth preparedness			0.5
subcomponent 1			3.5
HCP explained the			
possible danger signs that			
could occur during			
pregnancy	0 - No, 1 – Yes		
FD. 101101	1 110, 1 100		 

Birth preparedness			0.5
subcomponent 2			0.5
HCP discussed with the			
client where she will give	0 - No, 1 - Yes, -88 - Not		
birth	applicable		
HCP advised client to	аррисавіе		
prepare for birth (set aside			
money, arrange for	0 - No, 1 - Yes, -88 - Not		
emergency transportation)	applicable		
HCP advised client to use	аррисавіе		
a skilled health worker for			
	O No 1 Yes		
delivery	0 - No, 1 – Yes		
HCP discussed family	O No 1 Vos 80 Not		
planning for after the	0 - No, 1 - Yes, -88 - Not		
current pregnancy	applicable		
HCP advised pregnant	O No 1 Vac 99 Nat		
woman of the date for her	0 - No, 1 - Yes, -88 - Not		
next ANC contact	applicable		
Woman departure/exit time	[select time]		
Comments	-		
	[free text]		
PNC			
PNC - general			
Type of visit	1 - < 48 hours, 2- Day 6, 3-		
	Week 6,		
Women arrival time in the	[select time]		
facility			
Comments	[free text]		
PNC contact			
EC1b: Respectful			1
maternity care			
RMC subcomponent 1			0.25
The healthcare provider			
(HCP) introduced			
themselves to the			
postnatal woman	0 - No, 1 - Yes		
The HCP greeted the			
woman (or answered if			
woman greeted first)	0 - No, 1 – Yes		
RMC subcomponent 2			0.25
The HCP asked the woman	0 - No, 1 - Yes, -88 - Not		
to take a seat	applicable (no chairs)		
The HCP asked the woman	, , , , ,		
if she came with a			

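### The primary model in Section 3.8 has no visit-type term, although the tool records visit type and ANC contact type changes what earns points: a small, cheap precision gain is left unused

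*Protocol*

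**What the plan says.** Section 3.8 specifies a linear mixed model with a binary pre/post-training factor and "fixed effects for study month to account for any underlying secular trend". On clustering it states: "Random effects will be included for HCF (cluster), HCP within HCF and HCF by month interaction". The effect is to be reported as "adjusted (for month, HCF and HCF by month clustering) odds ratios (OR), with 95% confidence intervals". No visit-level covariate is named. The only mention of covariates is in the missing-data rule, which omits records lacking the outcome or "a covariate required for the analysis of that data value".

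Appendix 2 records visit type for both kinds of visit. The ANC form has a field "First/subsequent contact" with answers "0 - Subsequent contact, 1 - first contact -99 INF", followed by visit number and gestational age. The PNC form has a type-of-visit field whose answer list begins "1 - < 48 hours, 2- Day 6, 3" and continues with week 6.

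The ANC checklist then asks for different things by contact type:

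- **HIV and syphilis (EC5, EC6):** a test at the first contact or when the booklet shows no status; a status check where it is already recorded.
- **BMI (EC10):** measurement at the first contact; at later contacts a check of the earlier record can be enough.

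Section 3.4 counts all thirteen ANC components at every visit.

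**The concern.** The score is meant to reflect what the provider does. For three of the thirteen ANC components it also reflects which kind of visit the observer happened to see. Doing and noting a test is a different demand from reading a booklet, and the not-applicable answers remove questions without making the two tasks equal.

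Section 3.7 takes four consecutive clients per provider, and normally one observation day is scheduled per facility and period. Visit mix will therefore vary between facility-periods by chance. A model without visit type leaves that variation in the residual and facility-by-month terms. It also lets a chance difference in mix between pre- and post-training observations pass into the estimate. The variable that would remove this is already on the form.

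**Working it through.** **Inputs from the protocol**

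- Visit-level residual SD at most 0.2; each of the facility, provider and facility-by-month SDs at most 0.15; four visits per provider; three providers per facility; 18 facilities (Section 3.6).
- Sequences: Figure 1, three facilities per group.
- Share of first visits: Section 2.1.3 reports "6,936 ANC visits (of which 3,248 attending for the first/booking visit", so p = 3,248/6,936 = 0.468 and p(1 − p) = 0.249. This survey covered 60 facilities in twelve regions, so the share is only a stand-in for N'Djamena.

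**Assumptions**

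- Score gap d between first and later contacts of 0.1 to 0.2 (no document gives it).
- Two-sided 5% level, inferred from the 95% intervals.
- Correlation r of visit type within a facility-period of 0, with 0.3 as a sensitivity value (no source).

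**1. The plan's own figure.** SD = √(0.2²/4 + 3 × 0.15²) = √0.0775 = 0.278, and 0.81 × 0.278 = 0.225, which matches the stated 0.23.

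**2. Baseline for the comparison.** Generalised least squares on the Figure 1 design, with period effects and the SDs above, gives SE 0.0683. The detectable difference is (1.960 + 0.842) × 0.0683 = 0.191. This is below 0.23 because it uses the protocol's component SDs directly instead of the 0.81 multiplier from Table 4. Only the ratio with and without visit type matters here.

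**3. Effect of adjusting, r = 0.** Visit mix contributes 0.249 × d² to the visit-level variance, and adjustment removes it:

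| d | variance removed | residual variance of a four-visit mean | detectable difference | reduction |
|---|---|---|---|---|
| none | 0 | 0.0400/4 = 0.0100 | 0.1915 | – |
| 0.1 | 0.0025 | 0.0375/4 = 0.0094 | 0.1907 | 0.4% |
| 0.2 | 0.0100 | 0.0300/4 = 0.0075 | 0.1886 | 1.5% |

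**4. Sensitivity for d = 0.1 and 0.2**

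- All three random-effect SDs at 0.10, r = 0: 0.7% and 2.9%.
- All three at 0.05, r = 0: 1.6% and 6.6%.
- SDs at the 0.15 limit, r = 0.3 (a share r of the visit-mix variance then sits in the facility-period term): 1.6% and 6.6%.

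**5. Chance imbalance.** The shift in the estimate is approximately d × the pre/post difference in the share of first visits. For 10 points: 0.1 × 0.10 = 0.01 and 0.2 × 0.10 = 0.02. Weighting facility-periods as the planned model does, the chance SD of that difference is about 6 points at r = 0 and 12 points at r = 0.3 with three providers. A 10-point difference is therefore quite possible. Against the effect of 0.1 used in the Section 3.6 simulations, 0.01 to 0.02 is 10% to 20%.

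**6. PNC.** The only PNC item explicitly conditioned on visit timing is the date of the next contact, which is hidden at week 6. That is one question within one of sixteen components, so a smaller gain is likely.

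**The case against.** The strongest reply is that the model is a standard stepped-wedge analysis, that nothing in the protocol is contradicted, and that covariates are often left to an SAP. This stands in part: the analysis is valid without the term, and no figure in the protocol becomes wrong. But Section 3.8 does more than stay silent. It states what the effect is adjusted for, and visit type is outside that set.

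A second reply is that the scoring already handles visit type through not-applicable answers and alternative routes to the full point, and that some items work the other way. SP after the first trimester and fundal height after 16 weeks add requirements later in pregnancy. This also stands in part: the net gap may be small and its sign is unknown. With thirteen equally weighted components, a gap of 0.2 equals 2.6 whole components, so it is a generous upper value.

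A reader might infer that ignoring visit mix biases the training effect. The documents do not support this. Training dates are randomised by facility, so mix is balanced in expectation, and nothing describes booking-clinic days that would tie mix to training. Chance imbalance is sampling error, which the model's variance terms carry.

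A reader might also infer a large gain. A reduction of about 14% can be produced, but only with d = 0.2, r = 0.3 and a facility-by-month SD of 0.10 together. The gap and the clustering have no source, and the lower SD departs from the protocol's limit.

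Finally, adjustment has a hazard of its own. The contact field allows a -99 code, and the complete-case rule would then drop those visits. The fix must deal with this.

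**Conclusion.** The point holds as a modest, easily corrected weakness in the stated adjustment set. The cost of the omission is avoidable noise and exposure to chance imbalance; the analysis is neither biased in expectation nor invalid.

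For ANC, at the protocol's upper-limit SDs and without clustering of visit type, the term is worth about 0.4% to 1.5% of the detectable difference, and more if visit types cluster within observation days or the random-effect SDs are smaller. A chance 10-point difference in mix is worth 0.01 to 0.02 on the estimate. Both sizes rest on an assumed score gap of 0.1 to 0.2, and the precision figures also on a first-visit share taken from a wider set of facilities. For PNC no size can be given.

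I take the model to be fitted separately to ANC and PNC visits, as the two primary outcomes in Section 3.4 imply. The main argument for acting is that the gain is nearly free, and that prespecifying the term avoids a choice about adjustment after the mix is known.

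**What to change.** In Section 3.8:

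- Add first v subsequent contact as a prespecified fixed effect in the ANC model.
- Add visit timing (under 48 hours, day 6, week 6) as a prespecified fixed effect in the PNC model.
- Treat code -99 as its own category, or otherwise keep those visits, so that the missing-covariate rule drops no outcome data.
- Report the model without these terms as a sensitivity analysis.
- Do not add a gestational-age band. Estimating and noting gestational age is itself a scored component (EC11) that the training targets, so its recording may change with training.

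The cost is a few visit-level degrees of freedom and one extra analysis. No new data are needed.

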3.2 Trial type and design

3.2.1 Trial design

A multi-dimensional incomplete stepped wedge cluster randomised trial design (SW-RCT) in a cohort of HCPs will be used to assess the effects of the intervention (Training in ANC and PNC). The study duration will be 12 months with each step being 6 or 7 weeks in duration. Each HCF will receive the intervention (ANC-PNC training) and be observed following a defined schedule. The participants will be HCPs at the participating HCFs, for whom assessments are obtained in each assessment period through observing them in the provision of ANC-PNC services. The design is summarised in **Table 3**.

The benefits of the stepped wedge design in terms of feasibility and level of proof have been described previously (Hargreaves et al 2015, Hemming et al 2015, Prost et al 2015). Each HCF will provide data for both the control and the intervention state, which increases the efficiency of the trial. Estimates of intervention effects are expected to be more precise than in a parallel trial design.

Table 3: Summary of trial design

Intervention	Training in ANC and PNC
Design	Multi-dimensional incomplete SW CRT
	Cohort
Sampling units	Primary: 18 HCFs
	Secondary: 36 to 54 HCPs (2 to 3 per HCF and per step)
	Tertiary: clients (3 to 4 observations per HCP and per step)
Data measurement per HCF	Delivery of essential components during sampled ANC-PNC visits
No. and duration of steps	Six steps, eight assessment periods – each 1.5 months long (6-7 weeks)
Trial duration	12 months
Primary Outcome	Proportion of essential components delivered during ANC-PNC visits

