3.6 Sample size calculations

Number of HCPs for observation

The methodology knowledge base for stepped wedge trial designs is still relatively limited (Taljaard et al 2017). Quantities which need to be specified when designing them include: the number of clusters (HCFs) to participate; the number of steps; the number of steps per HCF in which assessments are made. For the current trial the number of HCPs to be observed and the number of assessments made per HCP per step are also needed. The most critical of these is the number of clusters to participate. Although the literature regarding sample size is in its infancy there is clear consensus that with few clusters the design lacks robustness (Barker et al, 2016 and Martin et al 2016). There are up to 20 HCFs available in which to conduct the trial. The incompleteness of the proposed trial design may compromise the integrity of the trial if fewer clusters are used. Thus, all available HCFs are planned to be included but calculation will be done on a minimum of 18 HCF for a conservative approach.

The number of steps possible is limited to six because it is not feasible to conduct more than six training sessions with the budget available. The duration of each step is set at six or seven weeks rather than one month to allow enough time for data collectors to accommodate with the observed HCP's roster and schedules within the appropriate steps.

In principle, the target number of HCPs for observation for each primary outcome should be three per HCF, however recognising this may not be feasible (especially in smaller facilities with limited staff present), the minimum number of HCPs to participate has been set at two per HCF, accepting that both HCPs would be required to take part in the trial and accept being observed completing both ANC and PNC visits in all four assessment periods planned for their HCF; this number is both feasible for this trial and expected to ensure adequate robustness to examine the hypotheses of interest (Girling and Hemming 2016).

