Observation of each HCP in multiple assessment periods will improve the power of the trial to detect an improvement in outcomes, since underlying differences between individual HCPs will be able to be modelled using random HCP effects. However, shift patterns will limit the availability of participating HCPs, so at some HCFs it may be necessary to conduct observations on two different dates within a step to be able to observe at least two HCPs in each assessment period. In facilities where both ANC and PNC clients are seen by each participating HCP observations for both primary outcomes will be able to be completed using the same HCPs. For other facilities, where ANC and PNC clinics are completed by different sets of staff on any given shift it may be preferable to recruit 4 to 6 HCPs, some to be observed providing ANC and others PNC. This would enable HCPs in both clinics to be observed on some observation days, thereby reducing the number of observation days in the assessment period. **Box 2** summarises the sample size planned.

Each interaction (ANC and PNC) observed will be assessed for the corresponding primary outcome.

The R shiny app ($\frac{\text{Hemming}}{\text{Memming}}$, 2019) was used in February 2020 to perform power calculations for this design, using a continuous response, with a standard deviation of σ . The standard deviation, σ , is the square root of the total variance, which aggregates the various components of variance. The app is not designed for the additional level of observation within HCP, so the data considered for purposes of sample size calculation is the mean across four observations for each HCP at the HCF.

Box 2: Sample size details

Number of clusters (HCFs):	18
Number of steps:	6 (8 assessment periods)
Duration of steps:	6-7 weeks
For each HCF:	
Number of HCPs per primary outcome*:	3 (or 2)
Number of periods in which care at HCF is assessed:	4
	(periods 1, 3, 5 and 7
	or 2, 4, 6 and 8)
Number of HCPs assessed for each primary outcome per assessment period:	At least 2
Number of HCP-client interactions assessed for each primary outcome per HCP assessed in an assessment period	4

^{*} where clinics combine ANC and PNC clients the same HCPs can be used for both; where ANC and PNC clinics are separate different sets of HCPs may be used.

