Delivery of essential components will be assessed through the observation of ANC-PNC visits by external data collectors. At each healthcare facility at least two healthcare providers will be observed in each assessment period. For each assessment period one observation day will be scheduled for each HCF to be assessed in the period. All participating HCPs on duty within the HCF will be observed completing four ANC/PNC visits on each of these days. If only one participating HCP is observed an additional observation day will be scheduled within the same assessment period to observe at least one more participating HCP within the HCF. Each HCP should be observed in at least three of the four assessment periods for their HCF. The observers will plan with the healthcare facilities to observe four consultations for each HCP who is on duty in accordance to rosters.

The availability of equipment and consumables for each component of care for ANC-PNC services quarterly (every 2 steps in the trial schedule) will be assessed on the first possible day of the following quarter. This data will allow for the analysis to assess if the delivery of essential components was linked or not by the availability of equipment and consumables. Finally, the number of women attending for and receiving care will be extracted quarterly

using the official routine facility registers. The healthcare facility assessment tool for equipment, consumables and use of services has been developed in line with the specific ANC-PNC service provision elements and with usual facility assessment tools used by CMNH-LSTM in baseline assessment (See **Appendix 3**).

Covid-19 situation

As of 13th of May, borders are closed and international flight barred, public transportation interrupted and meetings of 50 people or more prohibited. Our focal point from MoH and implementation partners from CSSI-CRASH consortium have so far not advised against conducting the study, which will be set only within N'Djamena and thus not require any interregional travels that may be impeded in the future. To date no other measures that could impede the delivery of this trial have been identified.

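### Section 3.8 models time by study month although the design and power run on eight assessment periods; read literally, this costs precision by default and can understate the SE where one facility-period spans two months

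*Protocol*

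**What the plan says.** Section 3.8 opens with a definition, "Period is defined as the assessment period of the trial which observation occurred", and the model that follows does not use it. The time effect is "fixed effects for study month to account for any underlying secular trend". The random part reads "Random effects will be included for HCF (cluster), HCP within HCF and HCF by month interaction". The reporting sentence again adjusts for month and for facility-by-month clustering.

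The rest of the protocol uses another unit. Section 3.2.1: "The study duration will be 12 months with each step being 6 or 7 weeks in duration", with "eight assessment periods" in Table 3. Figure 1 and Box 2 place training and observation by assessment period. Section 3.6 separates the two units itself: "The duration of each step is set at six or seven weeks rather than one month".

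On visit dates, section 3.7 schedules one observation day per healthcare facility (HCF) per period. If only one participating provider (HCP) was seen, "an additional observation day will be scheduled within the same assessment period". Section 3.6 adds that at some facilities "it may be necessary to conduct observations on two different dates within a step".

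**The concern.** Training status changes only between assessment periods, so the facility-period is the design's unit of replication over time. Twelve months divided by eight periods is 1.5 months per period, so each period covers one whole month and half of another. Months 2, 5, 8 and 11 each straddle two periods.

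Each facility is observed only in alternate periods. A facility-by-month term can therefore split a facility-period but cannot merge two. Where a split occurs, a shock common to the whole facility-period is modelled as two separate draws. The analysis then credits itself with more replication than it has, and the interval for the training effect can be too narrow. Where no split occurs, the extra time effects only use up information. In both cases the fitted model is not the one that was powered.

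**Working it through.** **1. What the power figure rests on.** I took 18 HCFs (three per group), Figure 1 with eight period effects, m HCPs per facility and 80% power from the protocol. Two-sided alpha of 0.05 is an assumption, consistent with the 95% intervals. For the four observed periods of one facility, V = ICC·C + ((1 − ICC)/m)·P. Here C has entries CAC^|s−t|, and P has 1 on the diagonal and IAC elsewhere. The SE comes from the inverse of ΣXᵀV⁻¹X, and the detectable difference is (1.96 + 0.842)·SE.

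- ICC 0.5, CAC 0.1, IAC 0.6: 0.811 with three HCPs (Table 4: 0.81) and 0.948 with one (Table 4: 0.95).
- All 20 cells of Table 4 agree within 3%. A constant (non-decaying) cluster correlation matches only 6 of 20.
- SD: √(0.01 + 3 × 0.0225) = 0.278, and 0.81 × 0.28 = 0.227, the protocol's 0.23.

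The power calculation therefore uses eight assessment periods.

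**2. How often a facility-period splits.** Assume months counted from trial start and dates uniform within the period. Two dates fall in different months with probability 2 × (2/3) × (1/3) = 0.44. One date never splits.

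**3. Effect on the SE.** The inputs are the section 3.6 upper limits: SD 0.15 (variance 0.0225) for HCF, HCP within HCF and HCF-by-time, and residual variance 0.01 for a mean of four visits. Three HCPs are seen per facility-period. The true covariance has the HCF-by-time term shared within a period; the fitted one has it shared within a month, with month fixed effects. With W the inverse of the fitted covariance and A = (ΣXᵀWX)⁻¹, the reported variance is the treatment element of A. The actual variance is that element of A(ΣXᵀW·V_true·WX)A. For r = reported SE / actual SE, type I error is 2[1 − Φ(1.96 r)].

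| Dates within a facility-period | Result for the month model | Type I error |
|---|---|---|
| One date everywhere | SE 0.072 against 0.068 by period (0.072/0.068 = 1.06) | 5% |
| Two in 25%, about a week apart | SE 2% too small | 5.5% |
| Two in 50%, about a week apart | 3% too small | 5.8% |
| Two in 25%, random | 4% too small | 6.0% |
| Two in 50%, random | 7% too small | 6.8% |
| Two in 100%, random, SD 0.07 | 8% too small | 7.0% |
| Two in 100%, random, SD 0.15 | SE 0.062 against 0.071, 14% too small before rounding | about 9% |

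**4. Check with estimated variance components.** I simulated REML fits with no true effect.

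- One date: mean SE about 0.071 by month and 0.067 by period; coverage by month about 94%.
- Two random dates in every facility-period: the month model's mean SE was 0.80–0.84 of its empirical SE, with coverage about 89%.
- Part of that shortfall is the usual small-sample one, since the period model's ratio on the same data was 0.95–0.99. Dividing run by run gives 0.799/0.951 = 0.84, 0.822/0.971 = 0.85 and 0.839/0.991 = 0.85, close to the 14% above.

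**5. A different truth.** If the facility effect decays continuously over time (time constant 0.5–2 months) and every facility-period has two random dates, the month model is only about 1–5% low. The period model then reports an SE 9–12% too large. Its actual SE is no larger than the month model's.

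**The case against.** The strongest reply is that month is only a loose word for period. Section 3.3 calls the training period a transition month, and section 3.6 names the per-step variance component HCF by month within a power calculation that uses eight periods. No section gives 12 time levels or says calendar month. On that reading the intended model is already the right one. This stands as a real possibility. But section 3.6 also says that a step is not a month, and section 3.8 defines period and then writes month three times, so an analyst following the text could fit either model.

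A reader might infer that the primary intervals will be too narrow as planned. The protocol does not support that. One observation day per facility-period is the schedule, and with it nothing splits and the SE is slightly larger. A second day is conditional in section 3.7 and expected only at some facilities in section 3.6.

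Some features make several dates plausible. Box 2 asks for four visits per HCP for each outcome, while section 3.10 caps observation at four per HCP per day. That alone splits nothing if ANC and PNC are analysed separately and each is observed on one day. PNC volume is a better pointer: 826 visits in 60 surveyed facilities is 826/60 = 13.8 per facility-month, or about 0.6 per day on an assumed 22 working days, against a target of 8–12 per facility-period. N'Djamena facilities may be busier, or may hold PNC on set clinic days, so this gives no frequency.

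It is also fair that shocks constant within a period are an assumption, and that Table 4 itself fits a correlation that decays over time. That reduces the understatement but does not favour month: in none of the scenarios run was the period model anti-conservative because of its time unit.

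**Conclusion.** The inconsistency is certain: section 3.8 specifies a time unit that conflicts with its own definition, with the design and with the power basis. Its consequence is conditional and moderate. Read literally, the month model loses about 5–6% in SE under the default single day. Where second dates fall in another month, the SE is understated by about 3–7% in the intermediate cases (2% in the mildest), with type I error of about 6–7%. The 14% understatement, with type I error near 9%, is an upper case. It needs two random dates in every facility-period and the SD at its 0.15 cap; at SD 0.07 the same dates give about 8%. These sizes assume months counted from trial start, all three HCPs observed and, except in step 5, a shock constant within the period. The frequency and spacing of second dates are my assumptions.

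**What to change.** In section 3.8, replace study month by assessment period (8 levels) in the fixed effects and HCF by month by HCF by assessment period in the random effects. Make the same change in the reporting sentence. If month was meant as period, this only clarifies the text.

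The cost is wording: the period follows from the schedule, and the survey date is already on the observation form. The one statistical downside is that intervals may be slightly conservative if facility effects drift within a period.
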